### **8.3            Lost to Follow-up**

A subject will be considered lost to follow-up if he or she repeatedly fails to return for scheduled visits and is unable to be contacted by the study site.

The following actions must be taken if a subject fails to return to the clinic for a required study visit:

- The site must attempt to contact the subject and reschedule the missed visit as soon as possible and counsel the subject on the importance of maintaining the assigned visit schedule and ascertain whether or not the subject wishes to and/or is able to continue in the study.
- In cases in which the subject is deemed lost to follow-up, the investigator or designee must make every effort to regain contact with the subject (where possible, 3 telephone calls and, if necessary, a certified letter to the subject's last known mailing address or local equivalent methods). These contact attempts are to be documented in the subject's medical record.
- If the subject continues to be unreachable, he/she will be considered to have withdrawn from the study with a primary reason of lost to follow-up.
- For subjects who are lost to follow-up, the investigator can search publicly available records (where permitted) to ascertain survival status. This ensures that the data set(s) produced as an outcome of the study is/are as comprehensive as possible.

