Endpoints: Secondary (3) – Duration-adjusted Event Rate of \geq Grade 2 Bleeding Events

The duration-adjusted event rate (**events/100 subject-years**) is defined as the number of grade ≥ 2 bleeding events, divided by the total duration (in 100 subject-years) that subjects have been on study from study day 1 to the earliest of last dose of IP + 30 days or EOS.

Bleeding events will be recorded on the adverse events case report form (CRF) and graded using the CTCAE version 5.0. Bleeding events will be identified using the narrow search of haemorrhages standardized MedDRA query (SMQ), using the MedDRA version 25.1 or later.

Abbreviations:

- b.events = Bleeding Events (Haemorrhages)
- Status = 1 (recurrence of b.event)
- Status = 0 (no b.event)

Censoring Rules:

- Subject with at least one or more than one “grade ≥ 2 b.events”
 - Subject may report multiple b.events, each b.event will be flagged with “Status = 1”.
 - Subject may report multiple b.events, if any b.event end date is missing then also “Status = 1”.
 - The treatment period from last b.event start date to Min(last dose of IP date+30, Study End date) will be considered as no event period, reported as “Status = 0”
- The subjects who do not report any “grade ≥ 2 b.events”
 - These subjects will be included in analysis with “Status = 0”.

Notes:

Status variable will be assigned considering “Haemorrhages” SMQ only, irrespective of number of other adverse event(s) experienced by subject.

- **Status is the censoring variable which will be utilized into the PHREG.**

Endpoints: Secondary (4) –Overall Survival

Overall survival time will be calculated from study day 1 to death. Subjects who have not died will be censored at their last date of contact.

Endpoints: Secondary (5) – Platelet Transfusion

Platelet transfusions during the treatment period is defined as a subject having at least one platelet transfusion after during study period as recorded on the transfusions CRF.

Endpoints: Secondary (6) – Achieving a platelet count $\geq 100 \times 10^9/L$

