Achieving a platelet count $\geq 100 \times 10^9/L$ at any time after study day 1, up to and including the date of the week 4 visit (ie, 7 days after the third planned dose of investigational product). if a platelet transfusion occurred during the 7 days preceding a platelet count, then that platelet count will not be considered as achieving the endpoint even if it is $\geq 100 \times 10^9/L$. Subjects who have no platelet counts during this period will be considered as not achieving achieved a platelet count $\geq 100 \times 10^9/L$. For subjects who never received IP, the subjects are considered as not achieving a platelet count $\geq 100 \times 10^9/L$. Weeks with no platelet count measurements (missing data) are considered as not achieving a platelet count $\geq 100 \times 10^9/L$.

Endpoints: Secondary (safety) – Myelodysplastic Syndromes (MDS) Free Time

Myelodysplastic syndromes (MDS) free time is defined as the time from the first dose of IP to the first occurrence of MDS. Subjects who have not had an MDS event will be censored at their last contact date or death date, whichever is later.

It is calculated as:

Date of first occurrence of MDS or censoring date – the date of the first dose of IP + 1.

MDS events will be identified using the narrow search of myelodysplastic syndromes (SMQ), using the MedDRA version **25.1** or later available at the time of the analysis.

Endpoints: Secondary (safety) – Myelodysplastic Syndromes (MDS) Free Survival Time

MDS free survival time is defined as the time from the first dose of IP to the first occurrence of MDS or death, whichever is earlier. Subjects who have not had an MDS event and have not died will be censored at their last contact date. It is calculated as:

Date of first occurrence of MDS, death or censoring – the date of the first dose date of IP + 1.

MDS events will be identified using the narrow search of myelodysplastic syndromes (SMQ), using the MedDRA version **25.1** or later available at the time of the analysis.

Endpoints: Secondary (safety) – Secondary Malignancy Free Time

[figure not shown]
Secondary malignancy free time is defined as the time from the first dose of IP to the onset of a secondary malignancy. Subjects without an event will be censored at their last contact date or death, whichever is later. It is calculated as:

Date of onset of secondary malignancy or censoring – the date of the first dose IP + 1.

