Endpoints: Secondary (safety) – Secondary Malignancy Free Survival Time

Secondary malignancy free survival time is defined as the time from the first dose of IP to the onset of a secondary malignancy or death, whichever is earlier. Subjects without an event will be censored at their last contact date. It is calculated as:

Date of onset of secondary malignancy, death or censoring – the date of the first dose date of IP + 1.

Last Contact Date

The latest date on which a subject is known to alive.

Myelosuppressive Treatment Agents

Myelosuppressive treatment agents are those agents in the on-study chemotherapy regimen that are 5-fluorouracil **or capecitabine and oxaliplatin (plus irinotecan in FOLFIRINOX or FOLFOXIRI) (Oxaliplatin)-based chemotherapy regimen.**

On-study Chemotherapy Regimens

The on-study chemotherapy regimen is the chemotherapy regimen planned to be taken after study day 1. It will be the same chemotherapy regimen taken in the last chemotherapy cycle immediately before study day 1.

Platelet Counts

If there are multiple platelet values performed on a study visit date, the platelet value most immediately prior to **non-IP** administration **will be selected**, as the platelet value for that study visit date. **If no platelet value prior to non-IP administration, the platelet value prior to IP administration will be selected.**

Prior Use of Medication at Baseline

Prior use of medication at baseline means the medication has been administered prior to the start of the current chemotherapy regimen.

Randomization Date

Randomization date is defined as the date the subject is randomized to a treatment group. Per protocol, subjects should initiate IP the same day they are randomized.

Study Day 1

Study day 1 is defined as the randomization date. **If the randomization date and the first IP administration date are the same, then study day 1 is the randomization date for both efficacy and safety analysis.**

If randomization date and subject first IP administration date are different then study day 1 will be derived using first IP administration date.

Study Day

For dates occurring on or after the study day 1 date, study day will be calculated as:

Date of interest - **date of first IP administration** + 1.

For dates occurring before the study day 1 date, study day will be calculated as:

Date of interest - **date of first IP administration.**

Treatment-emergent Adverse Event

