Appendix A. Code Fragment for Andersen-Gill Model

Duration adjusted bleeding event (Andersen-Gill Approach):

- K is strata for tumor type
- J is strata for baseline platelet count
- Tstart is time of the (k-1) recurrence for visit = k, or the entry time 0 if visit = 1, or the follow-up time if the (k-1) recurrence time does not occur
- Tstop is time of the kth recurrent if visit = k or follow-up time if the kth recurrence does not occur
- Status is bleeding status of Tstop (1=recurrence and 0=censored)
- txgrp is the treatment group variable:
 - active
 - placebo

PROC PHREG covs(aggregate);

Class J K txgrp;

MODEL (Tstart,Tstop)*Status(0)=Txgrp / ties=efron;

Strata K J;

Id usubjid;

Run;

Appendix B. Handling of Dates, Incomplete Dates and Missing Dates**Imputation Rules for Partial or Missing Start Dates**

The reference date for the following rules is the date of first dose[of study drug].

Start Date		Stop Date						Missing	
		Complete: yyyymmdd		Partial: yyyymm		Partial: yyyy			
		< 1 st dose	≥ 1 st dose	< 1 st dose yyyymm	≥ 1 st dose yyyymm	< 1 st dose yyyy	≥ 1 st dose yyyy		
Partial: yyyymm	= 1 st dose yyyymm	2	1	n/a	1	n/a	1	1	
	≠ 1 st dose yyyymm		2	2	2	2	2	2	
Partial: yyyy	= 1 st dose yyyy	3	1	3	1	n/a	1	1	
	≠ 1 st dose yyyy		3		3	3	3	3	
Missing		4	1	4	1	4	1	1	

1=Impute the date of first dose; 2=Impute the first of the month; 3=Impute January 1 of the year; 4=Impute January 1 of the stop year

Note: Note: If the start date imputation leads to a start date that is after the stop date, then do not impute the start date.

Imputation Rules for Partial or Missing Stop Dates

Initial imputation

- **If the month and year are present, impute the last day of that month.**
- **If only the year is present, impute December 31 of that year.**
- **If the stop date is entirely missing, assume the event or medication is ongoing.**

If the imputed stop date is before the start date, set stop date to missing.

If the imputed stop date is after the death date, impute as death date.

Death Dates, Secondary Malignancy Onset Dates, and MDS Onset Dates

If death/malignancy/MDS year and month are available but day is missing:

- If mmYYYY for last contact date = mmYYYY for death/malignancy/MDS date, set death/malignancy/MDS date to the day after the last contact date or EOS date, whichever occurs first.
- If mmYYYY for last contact date < mmYYYY for death/malignancy/MDS date, set death/malignancy/MDS date to the first day of the death/malignancy/MDS month.

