- If mmYYYY for last contact date > mmYYYY for death/malignancy/MDS date, data error and do not impute.

If both month and day are missing for death/malignancy/MDS date or a death / malignancy / MDS date is totally missing, do not impute.

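### SAP Appendix B leaves a known death with a year-only or missing date without an overall-survival time, so the death is not counted as an event

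*SAP*

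**What the plan says.** **Date rules (SAP Appendix B, block on death, secondary malignancy and MDS dates).** If only the day is missing, three cases are defined:
- Event month equal to the last-contact month: "set death/malignancy/MDS date to the day after the last contact date or EOS date, whichever occurs first".
- Event month later than the last-contact month: first day of the event month.
- Event month earlier than the last-contact month: "data error and do not impute".

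For anything less complete: "If both month and day are missing for death/malignancy/MDS date or a death / malignancy / MDS date is totally missing, do not impute".

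**Overall survival (SAP Section 5, secondary endpoint 4).** Time runs from study day 1 to death. "Subjects who have not died will be censored at their last date of contact". Last contact is defined in the same section: "The latest date on which a subject is known to alive". SAP Section 6.1 applies the full analysis set, meaning all randomized subjects, to the secondary efficacy endpoints. OS is the fourth secondary endpoint in the fixed test sequence (SAP Section 9.1). It is evaluated at the final analysis (SAP Section 7.3), whereas the study is unblinded at the primary analysis (SAP Section 7.2).

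**MDS and malignancy (SAP Section 5).** For MDS-free time: "Subjects who have not had an MDS event will be censored at their last contact date or death date, whichever is later". For malignancy-free time: "Subjects without an event will be censored at their last contact date or death, whichever is later".

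**Data collection.** For subjects lost to follow-up, Protocol Section 8.3 says "the investigator can search publicly available records (where permitted) to ascertain survival status". Protocol Section 9.2.3.4 requires vital status for all subjects within local law, using public databases if necessary, and asks for the date and cause of death.

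**The concern.** The OS rules provide for two kinds of subject: dead with a date, and not known to be dead. A third kind can arise, namely known to be dead without a usable date. Appendix B recognises this case but assigns it no date, and no other passage says how to analyse it. The programmer then has two options, and each breaks another rule of the plan. Leaving the time missing removes a randomized subject from an all-randomized analysis. Censoring at last contact treats a dead subject as alive.

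In both cases a known death is lost from a confirmatory secondary endpoint that stands ahead of platelet transfusion and platelet response in the sequence. The choice would also be made after unblinding, since OS is analysed at the final analysis. The same block governs MDS and malignancy onset, where its logic fits less well.

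**Working it through.** The plan gives no OS event count, OS effect size or rate of missing dates, so it has no figure to reproduce. The check has three parts.

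**1. Run each date pattern through Appendix B.** Illustration: last contact 10 March 2022, EOS 30 June 2023.

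| Recorded death date | Appendix B result |
|---|---|
| 4 May 2022 | 4 May 2022 |
| March 2022 | 11 March 2022 |
| May 2022 | 1 May 2022 |
| February 2022 | none (data error) |
| 2022 | none |
| 2023 | none |
| wholly missing | none |

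The last four patterns give no event time. The February pattern contradicts the last-contact date and is properly queried for a death. The other three contain no contradiction, and last contact already supplies a lower bound for each.

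**2. Effect on the hazard ratio (HR, romiplostim vs placebo).** Simulation of 3,000 trials per scenario with an unstratified Cox model and true HR 1.
- From the documents: 108 and 54 subjects. Censoring is uniform over 14 to 50 months, the range of study duration in Protocol Section 5.3.2.
- Assumed: exponential survival with median 18 months, which gives about 111 deaths. Last contact falls 0 to 2.8 months before death, in line with 12-weekly contacts.
- Assumed: the shares of deaths left undated, as in the table.

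Ratio of the resulting HR to the full-data HR:

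| Undated: romiplostim / placebo | Mean undated deaths | Subject dropped | Subject censored | Dated the day after last contact |
|---|---|---|---|---|
| 5% / 5% | 5.6 | 1.000 | 1.001 | 1.000 |
| 2% / 10% | 5.2 | 1.044 | 1.085 | 0.996 |
| 10% / 2% | 8.2 | 0.957 | 0.923 | 1.004 |

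Equal loss does not move the HR. More loss on placebo shifts it against romiplostim, and more loss on romiplostim shifts it in favour.

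**3. Effect on power.** Schoenfeld approximation for D deaths, 2:1 allocation, two-sided 0.05:

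power = Φ( √(D × 1/3 × 2/3) × |ln HR| − 1.96 )

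With an assumed HR of 0.7, |ln HR| = 0.357:
- D = 100: 4.714 × 0.357 − 1.96 = −0.28, power 39.0%.
- D = 96 (4 deaths lost): power 37.7%.
- D = 92 (8 deaths lost): power 36.4%.

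Over 60 to 120 deaths and HR 0.6 to 0.7, losing 8 deaths costs about 2.5 to 5 percentage points.

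**The case against.** **The protocol works against the problem.** Section 9.2.3.4 asks for the date of death, including for subjects who stopped visits. Long-term contacts are every 12 weeks. Serious adverse events are collected through end of study, and the contingency form asks for the date of death as the end date of a fatal event. This stands, and it is why the number affected is probably small. It does not remove the case, and Appendix B itself foresees it.

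**Not imputing is not the same as excluding.** This is correct. The SAP never says that these deaths are dropped or censored, and that consequence is inferred. But the instruction leaves no permitted way to count the death.

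**A reader might infer that undated deaths will be more frequent on placebo.** SAP Section 8.4 does not support this. It says only that placebo subjects might drop out earlier, and it ties this to disposition and exposure tables and to sensitivity analyses of the primary endpoint. Subjects who stop investigational product remain in follow-up, so early dropout is not the same as a missing death date.

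**A reader might also infer that MDS and malignancy events disappear from the safety analysis.** They do not. SAP Section 9.7 tabulates them as number and percentage, which needs no date. In the event-free survival versions, a later dated death still counts as an event. The effect is confined to descriptive time-to-event summaries.

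**Conclusion.** The point holds as a minor defect in a stated rule. Following Appendix B, a known death with a year-only or wholly missing date has no OS time and is not counted as an event. This conflicts with the plan's own censoring rule or with its all-randomized analysis set.

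The likely effect is small. With a few undated deaths spread evenly over the arms, the HR is essentially unchanged and the power loss is 1 to 5 points across the cases examined. Material bias requires the undated share to differ by arm, and no document establishes that it will. The size estimates rest on the assumed number of deaths, HR and undated shares. OS is formally tested only if the primary endpoint and three earlier secondary endpoints succeed.

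The good performance of dating a death to the day after last contact holds only where contact was recent. It was not tested for subjects lost for a long time, in whom that date may fall well before death.

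**What to change.** Amend Appendix B and separate deaths from the other two events.

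**Deaths**
- Year only: the later of 1 January of that year and the day after last contact, capped at EOS. If last contact falls after that year, raise a data query.
- Date wholly missing but death confirmed: the day after last contact or EOS, whichever is first. Use the same rule for a death whose date query cannot be resolved.
- State that EOS here means the end of the trial. A subject-level end date could precede a death found later in public records.
- Count these deaths as events, flag them, and list them by arm.
- Add a sensitivity analysis at the latest possible date: 31 December of the known year, or EOS/data cut-off if that is earlier or the year is unknown.

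In the illustration above, year-only 2022 becomes 11 March 2022, year-only 2023 becomes 1 January 2023, and a wholly missing date becomes 11 March 2022.

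**MDS and secondary malignancy**
- Write an onset rule that is not anchored after last contact. One option for year-only dates is the later of 1 January of that year and the first dose of investigational product, and not after death or last contact. The death rule must not be reused: a malignancy known to date from 2021 in a subject last contacted in June 2023 would be placed in June 2023.
- Stop treating an onset month before the last-contact month as a data error. Such onsets are ordinary in living subjects.
- State that this rule overrides the general start-date table in the same appendix, which does impute year-only dates.

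The cost is a few lines of text and one sensitivity analysis, with no new data. The downside is a small dating error toward earlier death in subjects lost for a long time, which the sensitivity analysis brackets. The change should be made before unblinding at the primary analysis.
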